### **6.2 Sample Size**

While our primary interest is in assessing the value of an intensive motor training program for improving measures of function, we are also interested in assessing between-groups differences in those who do versus do not receive tDCS to augment training. Our primary outcome measures are related to walking function. Sample size calculation is based on our published study from participants trained with intensive motor training alone, wherein the improvement in walking speed had an effect size of 0.69.[15] Based on this effect size, in order to identify pre-post differences due to training using the full study sample, a sample size of 15 participants is required to obtain a power of 0.8 with  $\alpha = 0.05$ . However, since we are also interested in between-group differences between the MT+tDCS and MT-only groups, if we assume an additive or larger effect of the tDCS, it will be necessary to double the sample size to 30, with 15 participants per group to identify significant between-groups differences at the same power and alpha levels. To accommodate an anticipated 15% attrition rate we will enroll 35 participants.

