### **6.1 Statistical Assumptions**

All data will be managed using Microsoft Excel and analyzed using SPSS. Descriptive statistics, including means, standard deviations and 95% confidence intervals of the pre-post change for each condition will be calculated for all measures. The baseline characteristics of the participants assigned to the 2 intervention groups will be compared using ANOVA and Chi-square analysis. The change from Baseline test (day 1) to Persistence test (day 5) for the two intervention groups will be compared using repeated measures ANOVA followed by pair-wise contrasts between the two groups. Pair-wise t-tests with Bonferroni correction for multiple comparisons will be used to evaluate within-day change for each of the 3 intervention days. We will identify the effect size and 95% confidence interval associated with effects to identify the outcome measures that are most sensitive to change following intervention with MT-only and MT+tDCS. We will also assess variables associated with responsiveness to intervention, using logistic linear regression to identify the variables that are most strongly associated with change in our primary outcome measure of walking function. Where significant pre/post differences exist among the primary outcome measures and blood serum concentrations of BDNF, Pearson correlation coefficients will be calculated to determine the strength of any relationship that might exist between measures of walking function and changes in BDNF concentration.

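### Section 6.2's pre-post sample size of 15 for 80% power holds only for a one-sided test; no one-sided test is declared, and a conventional two-sided paired t-test has 70% power at 15 and needs 19

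*Combined protocol and SAP*

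**What the plan says.** Section 6.2 (Sample Size) takes its input from a published study of intensive motor training alone, "wherein the improvement in walking speed had an effect size of 0.69". From that figure it derives the number needed "in order to identify pre-post differences due to training using the full study sample", and concludes that "a sample size of 15 participants is required to obtain a power of 0.8 with" alpha set at 0.05. It attaches no sidedness to the alpha and does not define the effect size. The next sentence doubles the 15 to 30, at 15 per group, for the comparison of MT+tDCS with MT-only, and claims the same power and alpha. Enrolment is then set at 35.

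Section 6.1 (Statistical Assumptions) plans "means, standard deviations and 95% confidence intervals of the pre-post change for each condition will be calculated for all measures". For the change from baseline to day 5, the two intervention groups "will be compared using repeated measures ANOVA followed by pair-wise contrasts between the two groups". For within-day change it plans "Pair-wise t-tests with Bonferroni correction for multiple comparisons". It does not say one-sided or two-sided for any of these.

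**The concern.** An alpha of 0.05 without qualification, next to 95% confidence intervals, will be read as two-sided. On that reading the 15 does not give the stated power for a paired comparison at an effect size of 0.69, so the plan's power statement does not describe the tests that readers will assume.

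Two things are at stake. The sentence is the power justification for what section 6.2 calls the study's primary interest, the value of the training programme. The 15 is also reused: it becomes the per-group number, and then the basis of 30 and 35. An error in the first figure therefore affects how the later figures are justified, even if the enrolled number is ample for the training effect itself.

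**Working it through.** **Inputs from section 6.2:** effect size 0.69, alpha 0.05, target power 0.80, stated n = 15, planned completers 30.

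**Assumption:** 0.69 is d = mean change / SD of change. The document does not define it.

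**Formula.** For a paired t-test on n participants, df = n − 1 and the noncentrality is d × √n. One-sided power is the probability that a noncentral t exceeds the upper 5% point of t. Two-sided power uses the upper 2.5% point and adds the negligible opposite tail.

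**Step 1: reproduce the plan's figure (one-sided, alpha 0.05).**
- n = 14: noncentrality 0.69 × √14 = 2.582, critical value 1.771, power 0.788.
- n = 15: noncentrality 0.69 × √15 = 2.672, critical value 1.761, power 0.815.

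The smallest n that reaches 0.80 is 15, exactly the stated figure.

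**Step 2: the same calculation, two-sided, alpha 0.05.**
- n = 15: noncentrality 2.672, critical value 2.145, power 0.701.
- n = 18: noncentrality 0.69 × √18 = 2.927, critical value 2.110, power 0.788.
- n = 19: noncentrality 0.69 × √19 = 3.008, critical value 2.101, power 0.812.

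The smallest n is 19, which is 4 more than stated (4/15 = 27%).

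**Step 3: could rounding or another two-sided method give 15?**
- Effect sizes that round to 0.69 (0.685 to 0.695) leave both minima unchanged: 15 one-sided and 19 two-sided. Two-sided power at 15 runs from 69.4% to 70.7%.
- The normal approximation, ((1.960 + 0.842)/0.69)² = 16.5, gives 17, with power 76.2% at 15. It ignores the t distribution and is too optimistic at this size. Adding the usual small-sample term 1.960²/2 = 1.92 gives 18.4, so 19.
- A signed-rank test, approximated through its relative efficiency of 3/π, needs 20 and has 68.1% power at 15.

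None of these two-sided methods reaches 0.80 at n = 15.

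**Step 4: what the planned sample delivers, two-sided.**
- n = 30: noncentrality 0.69 × √30 = 3.779, critical value 2.045, power 0.955.
- At n = 30, 80% power is reached at d = 0.53.

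**The case against.** The strongest reply is that section 6.1 never says two-sided. Its confidence intervals stand in a sentence on descriptive statistics. Its repeated measures ANOVA is described as a comparison of the two intervention groups, and its t-tests address within-day change; neither is the pooled pre-post test that the 15 refers to. The hypotheses in section 2.1 are directional, expecting improvement. The authors may have intended a one-sided test, in which case 15 is correct. This stands in part: two-sidedness is inferred from convention and from the absence of any one-sided declaration. It does not rescue the text, because a one-sided 0.05 test has to be declared and the document nowhere does so.

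A second reply is that reading 0.69 as mean change over SD of change is partly circular. The reading is supported because it reproduces 15, but only with a one-sided test. That is fair, and the definition has to remain a stated assumption.

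Third, the consequence is small. That also stands: 15 is not the planned sample, and 30 completers are ample for the training effect at 0.69.

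A reader might go further in three ways that the document does not support:
- **A larger requirement for the within-day tests.** Section 6.1 does not give the Bonferroni divisor, and section 6.2 neither sizes the study for those tests nor says that 0.69 applies to a single-session change.
- **An error in the attrition allowance.** The plan says "To accommodate an anticipated 15% attrition rate we will enroll 35 participants". Since 35 × 0.85 = 29.75, the gap from 30 is less than one participant, which is rounding.
- **A new total of 38, by doubling 19.** This would keep the doubling argument, which carries a pre-post calculation over to a different comparison. It is not a basis for changing enrolment.

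**Conclusion.** The point holds as a minor correction. As written, the statement that 15 participants give power 0.8 at alpha 0.05 is true only for an undeclared one-sided test. Under the conventional two-sided reading, power at 15 is 70% and the requirement is 19.

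This rests on two assumptions: that 0.69 is the mean change divided by the SD of change, and that the tests are two-sided, which section 6.1 implies but does not state.

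A reader might infer that the training aim is underpowered or that more participants are needed. The plan's own numbers do not support that: 30 completers give about 95% two-sided power at 0.69. What is wrong is the stated figure and its use as the foundation for 30. Whether 30 suffices for the between-group comparison is a separate question, which this check does not settle.

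**What to change.** 1. State in sections 6.1 and 6.2 that all tests are two-sided. If a one-sided pre-post test was intended, the plan must declare and justify it instead.
2. Replace the pre-post sentence in section 6.2 with: *Two-sided paired t-test, alpha 0.05: 19 participants give 80% power for d = 0.69 (mean change divided by SD of change); the planned 30 completers give about 95% power at d = 0.69 and 80% power for d = 0.53.* Confirm from the source study that 0.69 is on this scale.
3. Reword the following sentence so that 30 is no longer presented as a doubling of 15, and do not carry the 0.8 power claim over from the pre-post calculation. Without this step the paragraph would contradict itself once 15 becomes 19.

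Enrolment stays at 35. The cost is a wording amendment: no additional participants, visits or measurements. The stated minimum becomes less favourable, but the justification for the training aim becomes stronger and reproducible.

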A preponderance of the evidence suggests that corticospinal drive is increased by **combining** moderately intense motor training with stimulation of supraspinal centers. This notion is supported by research demonstrating that intensive motor training aimed at increasing corticospinal drive improves muscle activation and walking function.[15] Furthermore, non-invasive brain stimulation has been shown to improve lower extremity strength, lower-limb control, gait, and balance.[16-19] Cortical stimulation with repetitive transcranial magnetic stimulation (rTMS) has been associated with improved walking function in persons with SCI [20], although this form of stimulation has inherent drawbacks that limit its use in clinical settings. An alternative to rTMS is transcranial direct current stimulation (tDCS), which is a low-risk, non-invasive brain stimulation technique involving low-intensity currents delivered to the motor cortex and aimed at modulating cortical excitability. tDCS is affordable and lacks many of the drawbacks associated with rTMS, making it a more clinically accessible technology. Emerging studies in persons with stroke have combined tDCS with moderately intense motor training and have demonstrated increased dorsiflexor control,[16] quadriceps strength,[17, 18] and balance.[17] tDCS may also have the capacity to modulate excitability of spinal networks and to decrease spasticity.[21, 22]

Based on the evidence described above, we put forward two primary goals of the proposed project: *1) determine whether a moderate-intensity training program designed to increase control of gait-related movements can improve functional and neurophysiologic measures, and 2) determine whether training-related responses are larger when training is augmented with cortical stimulation to increase supraspinal drive.*

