#### 3.2.1 Research Design:

We propose a double-blinded, randomized, cross-over intervention study consisting of a moderate-intensity motor training circuit of gait-related upright motor control activities. We will also assess whether the addition of tDCS augments the training-related gains. Effects of training (and tDCS) on walking function, balance, strength, and spasticity will be assessed to determine whether there is preliminary evidence of efficacy of this approach.

**Stratified randomization:** To ensure equivalence of baseline data between groups, stratified randomization will be used. We have shown that persons with SCI who are ambulatory may be classified into one of two groups, with “**less impaired**” participants having lower limb motor scores of >15 for one leg and ≥10 for the other leg; participants not meeting this criteria are classified as “**more impaired**”. To ensure equivalent distribution of more- and less-impaired participants between groups, individuals will be stratified into one of these two strata based on the above criteria, with randomization to groups within each stratum.

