#### Schedule of Events:

[figure not shown]
Individuals will be asked to participate in the study over two, 5 consecutive day periods. Following completion of the fifth day, participants will be asked to take 2 weeks off before returning to the lab to repeat the intervention schedule but in the opposite group in which they originally participated (i.e. MT-only to MT+tDCS; MT+tDCS to MT-only). A detailed schedule of events including testing and intervention timing is provided in Figure 1.

**Figure 1.** Timing of intervention and outcome measures.

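### Section 6.2 gets its power for MT+tDCS versus MT-only by doubling a one-sample n of 15, which is invalid, and it assumes two parallel groups although the trial is a cross-over

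*Combined protocol and SAP*

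**What the plan says.** Section 6.2 starts from an earlier study of motor training alone, "wherein the improvement in walking speed had an effect size of 0.69". On that basis, for the pre-post change in the full sample, "a sample size of 15 participants is required to obtain a power of 0.8 with" alpha 0.05. It then turns to MT+tDCS versus MT-only: "if we assume an additive or larger effect of the tDCS", then "it will be necessary to double the sample size to 30, with 15 participants per group to identify significant between-groups differences", at unchanged power and alpha. Enrolment is set at 35 to allow for 15% attrition. The section gives no number for the tDCS effect, no sidedness and no within-person correlation.

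Section 3.2.1 describes a "double-blinded, randomized, cross-over intervention study". Under Schedule of Events, participants take two weeks off and then "repeat the intervention schedule but in the opposite group in which they originally participated".

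Section 6.1 says that the Day 1 to Day 5 change "for the two intervention groups will be compared using repeated measures ANOVA followed by pair-wise contrasts between the two groups". Section 1.0 lists the tDCS question as one of two primary goals: to "determine whether training-related responses are larger when training is augmented with cortical stimulation to increase supraspinal drive".

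**The concern.** There are two separate faults in 6.2.

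- **The arithmetic.** The 15 is a one-sample n. A difference between two independent means has twice the variance of a single mean at the same n per group. Detecting the same standardised effect therefore takes about twice as many participants in each group, or four times as many in total. Doubling the total to 15 per group does not preserve 80% power.
- **The design.** Fifteen per group describes a parallel trial. In the cross-over, 30 completers give 30 within-person pairs, and power depends on how strongly a person's two changes are correlated. Section 6.2 does not use that quantity.

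Section 6.1 does not close the gap. It does not say that condition is a within-participant factor, and it names no period or sequence term.

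At stake is one of the two primary goals, and the tDCS comparison is also the plan's reason for going from 15 to 30. A reader cannot tell what tDCS increment the trial can detect, and a null result could be misread as coming from a comparison with 80% power.

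**Working it through.** **Inputs from section 6.2:** effect size 0.69, alpha 0.05, power 0.80, n = 15 pre-post, 15 per group between conditions, 15% attrition, 35 enrolled (35 × 0.85 = 29.75, about 30 completers).

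**Assumptions, not in the documents:** 0.69 is mean change divided by SD of change; the tDCS increment is a further 0.69 SD; carry-over is negligible; ρ, the correlation between a person's two changes, ranges from -0.3 to 0.5. All power values use the exact noncentral t unless marked as simulation.

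**Step 1. Reproduce the plan's 15.** One-sample t, noncentrality d√n = 0.69 × √15 = 2.67, df 14.

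| n | one-sided power | two-sided power |
|---|---|---|
| 14 | 0.788 | 0.666 |
| 15 | 0.815 | 0.701 |
| 18 | 0.878 | 0.788 |
| 19 | 0.894 | 0.812 |

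The plan's 15 reproduces exactly, but only one-sided; a two-sided test needs 19. This matters little for the training question, because 30 completers give two-sided power 0.955.

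**Step 2. Two independent groups of 15, as 6.2 describes.** Noncentrality d√(n/2) = 0.69 × √7.5 = 1.89, df 28. The noncentrality falls from 2.67 by a factor of √2, which is why doubling the total fails.

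| | two-sided | one-sided |
|---|---|---|
| Power, 15 per group, 0.69 SD | 0.446 | 0.579 |
| n per group for 0.80 | 34 | 27 |
| Increment detectable at 0.80, 15 per group | 1.06 SD | 0.93 SD |

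The 15 per group does not reproduce at 0.69 SD under either sidedness.

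**Step 3. The cross-over, 30 completers, period-adjusted within-participant contrast.** The SD of the difference between a person's two changes is √(2(1-ρ)) in SD-of-change units. The noncentrality is 0.69 × √30 / √(2(1-ρ)), with df 30 - 2 = 28.

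| ρ (assumed) | noncentrality | power two-sided | power one-sided | increment detectable at 0.80, two-sided |
|---|---|---|---|---|
| -0.3 | 2.34 | 0.62 | 0.74 | 0.85 SD |
| 0 | 2.67 | 0.73 | 0.83 | 0.75 SD |
| 0.3 | 3.19 | 0.87 | 0.93 | 0.63 SD |
| 0.5 | 3.78 | 0.95 | 0.98 | 0.53 SD |

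Power reaches 0.80 at ρ of about 0.15 two-sided, or -0.10 one-sided.

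**Step 4. What the gap in 6.1 could cost (illustrative, by simulation of 40,000 trials, two-sided).** If the 30 changes per condition were treated as independent, power at ρ 0.3 and 0.5 would be 0.79 and 0.82, against 0.87 and 0.95 when paired. If the analysis were paired but had no period term, and the period effect were 0.69 SD (an assumed value), power at ρ 0, 0.3 and 0.5 would be 0.65, 0.79 and 0.89, against 0.73, 0.87 and 0.95 with the term.

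**The case against.** The strongest reply is that 0.45 and 0.58 are powers for a design nobody will run, at an increment the plan never states. An additive effect can mean only that tDCS contributes something of its own on top of training, with no tie to 0.69. A larger effect is also allowed, and 15 per group does reach 0.80 at 0.93 SD one-sided, the sidedness that reproduces the plan's own 15. The cross-over may well be adequately powered. Section 6.2 puts training first, and section 3.2.1 seeks only preliminary evidence. Repeated measures ANOVA is also compatible with condition as a within-participant factor.

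Part of this stands. The 0.45 and 0.58 must not be read as the trial's power, and 0.69 SD is our reading. Section 6.1 is underspecified rather than shown to be unpaired, and the period effect in step 4 has no source in the documents.

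The reply does not rescue 6.2. The plan states no increment at which 15 per group would be right, and it offers no calculation for the design it runs. Section 1.0 also makes tDCS augmentation a primary goal. That the cross-over might suffice depends on a correlation and an analysis model that the plan does not state.

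**Conclusion.** The concern holds. The pre-post 15 is sound if one-sided, but the move to 15 per group is not a valid two-sample calculation and does not describe the cross-over. On the parallel reading with a 0.69 SD increment, power is 0.45 two-sided or 0.58 one-sided, not 0.80.

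This does not show that the trial is underpowered. For the design being run, two-sided power at 0.69 SD lies between 0.62 and 0.95 across the assumed correlations, provided that the analysis is within participant and adjusted for period. The figures rest on 0.69 being in SD-of-change units, about 30 completers and negligible carry-over. The fault in the arithmetic and the mismatch with the design do not depend on the correlation. Because the stated power supports a primary goal, it must be corrected.

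**What to change.** Keep 35 enrolled.

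**In section 6.2:**
- Delete the doubling to 15 per group.
- State whether alpha 0.05 is one-sided or two-sided; if two-sided, the pre-post 15 becomes 19.
- State the assumed tDCS increment and the between-period correlation (or the SD of the within-person difference), with their source.
- Restate power for the within-participant contrast of Day 1 to Day 5 walking-speed change. A template, to be filled with the sponsor's own inputs:

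> About 30 completers give 80% two-sided power for a tDCS increment of 0.75, 0.63 or 0.53 SD of change at an assumed between-period correlation of 0, 0.3 or 0.5 (0.85 SD at -0.3), assuming negligible carry-over and that 0.69 is in SD-of-change units. The same 30 give about 95% power for a pre-post effect of 0.69.

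**In section 6.1:** add one sentence saying that MT+tDCS and MT-only are compared within participant, with condition as a within-participant factor and a term for period.

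The cost is a rewording of 6.2 and one sentence in 6.1, with no added participants or visits. The drawback is that the stated tDCS power becomes openly conditional on an assumed correlation and on negligible carry-over.

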### 6.3 Project Implementation Plan

Table 3 provides a summary of the project implementation plan.

Table 3. Project Implementation Plan	Timeline (Mths)	Investigator(s)
Major Task 1: Management Activities		
Prepare regulatory documents and research protocol for the study. Modify the study according to Shepherd Center RRC recommendations.		
Refine eligibility criteria, exclusion criteria, screening protocol	1-3	EFF/NE
Finalize consent form & human participants protocol	1-3	EFF/NE
Submit RRC protocol for review	1-3	EFF/NE
Submit protocol for IRB approval	1-3	EFF/NE
Submit amendments, adverse events, and protocol deviations as needed	As Needed	NE
Annual IRB report for continuing review	Annually	EFF/NE
Major Task 2: Coordination Activities		
Coordinate training of project staff	1-6	EFF/NE
Coordinate supervision and fidelity checks as needed for attrition	Quarterly	EFF
Major Task 3: Research Activities		
Coordinate all study steps, data collection and database requirements	3-6	EFF/NE/BP
Finalize assessment measurements	3-6	EFF/NE
Begin participant recruitment	6	NE
Perform participant baseline evaluations/assessments	6-42	NE
Participants complete assigned intervention and “immediate effects” measured	6-42	NE
Participants complete “persistent effect” measurements	6-42	NE
Major Task 4: Data Analysis Activities		
Monitor data collection procedures and data quality	6-42	EFF/NE/BP
Perform all analyses according to specifications, share output and findings with study investigators	42	EFF/NE
Major Task 5: Dissemination Activities		
Prepare manuscripts, abstracts, and presentations	43-48	EFF/NE
Submit manuscripts, abstracts, and report findings at relevant national/international conferences	43-48	EFF/NE
Abbreviations: IRB (Institutional Review Board); EFF ([name]); [name] (NE); [name] (BP);		

